Hospital admissions involves staying at a hospital for at least one night or more for medical reasons. It includes admissions to hospital wards and overnight stays in emergency departments.

Sample size

The sample size was calculated on the basis of the primary hypothesis. A total of 1050 HCW randomized with an estimated loss to follow-up of 5%, and a mean number of days off work due to illness in the control group of 5 days (SD=5) over a 6-month period will demonstrate a reduction among BCG vaccinated of 20% for a mean absence of 4 days (80% power and alpha 0.05). The estimated loss to follow-up (5%) was based on past telephone-based surveys conducted in Mozambique and Bissau.

Assignment of interventions

Randomization

All participants who give consent for participation and who fulfil the inclusion criteria will be randomly assigned to either placebo or BCG group with a 1:1 (treatment:placebo) allocation in blocks of 4 to 6 within strata defined by gender (male/female) and occupational group (doctors/nurses/other).

Blinding

The BCG vaccine will be administered by study physicians/nurses, who are not blinded but also not involved in the data collection. Participants, data collectors and data entry clerks will be blinded to the treatment allocation. In case of serious adverse events, the participant can be unblinded after consultation with the investigator or the vaccinating physician/nurse.

When the study has ended, all participants will receive information about the intervention that they received.

Data collection

Data collection instruments include: consent form, inclusion/exclusion criteria form, baseline questionnaire, follow-up questionnaire, and end questionnaire.

Variables

The endpoint variables are described in

Table 1.

Table 1 – Definition of end-point variables

Variables	Definition	Type	Scale	Domain
Absenteeism	Refers to the total number of days absent from work due to illness	Quantitative	Numeric	In days

Variables	Definition	Type	Scale	Domain
Absenteeism for COVID-19	Refers to the number of days absent from work due to COVID-19	Quantitative	Numeric	In days
Absenteeism besides COVID-19	Refers to the number of days absent from work due to diseases /illness besides COVID-19	Quantitative	Numeric	In days
Absenteeism for infections	Refers to the number of days (unplanned) absent from work due to infections	Quantitative	Numeric	In days

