Other Outcomes Measures: Hospitalisation for COVID-19; hospitalisation for respiratory infections; COVID-19 infection episodes; Furthermore, we will study the effect on Death for any reason, Death due to documented COVID infection. Cumulative incidence of infectious disease episodes, in particular respiratory infections. Cumulative incidence of infectious hospital admissions, in particular respiratory infections. Cumulative incidence of hospital admission due to documented COVID-19. Cumulative incidence of all-cause and infectious intensive care admission. Cumulative incidence of intensive care admission due to documented COVID infection.

Baseline data collection

Enrolment data regarding chronic illnesses and treatment, lifestyle (family structure, socioeconomic factors, smoking), vaccination history including previous BCG vaccination. Blood sample for SARS-CoV-2 serology.

Follow-up

Follow-up will last for 6 months (182 days). Telephone interviews every second week, regarding symptoms, absenteeism and causes, COVID-19 testing (if done) and their results. Supplemented by daily workplace presence registry information (where present).

End of follow-up

At the end of follow-up, participants will be invited back to the room of the healthcare facility where they were recruited to have another SARS-COV-2 antibody test and to complete the final questionnaire; also, at this time, the research officer will be asked to inspect and report how scarification is in the deltoid area of the right upper limb of the HCW, which may occur due to the BCG vaccine. Information regarding the treatment (BCG or placebo) will be disclosed to the participant at this time.

Sample size

The sample size was calculated on the basis of the primary hypothesis. A total of 1050 HCW randomized with an estimated loss to follow-up of 5%, and a mean number of days off work due to illness in the control group of 5 days (SD=5) over a 6-month period will demonstrate a reduction among BCG vaccinated of 20% for a mean absence of 4 days (80% power and alpha 0.05). The estimated loss to follow-up (5%) was based on past telephone-based surveys conducted in Bissau.

Statistical analysis.

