- **Randomized ("chosen at random")**: This is any randomization procedure (in our study we will use a computer program - REDCap - for the randomization of participants. In this way, all subjects participating in the trial will have strictly the same probability of receiving the BCG vaccine or the one corresponding to the study control (placebo).

- **Absenteeism** is referred to as the total number of absences (in days) of the health worker care due mainly to some illness.

3. Sample size

Our sample size was defined based on the calculations made by the Dutch group which computed in 1000 the minimum sample size. We decided include 350 participants per site(Cape Verde, Guinea Bissau and Mozambique) which adds 1050 participants. This participants number is near enough to show significance for the primary outcome - expected absenteeism reduction from 5% to 4%.

Based on current experience, the investigators consider that this a feasible sample size, which well balances burden of participants against public interest. As this is an adaptive study, the final follow-up duration is subject to the percentage of absenteeism during the study period, variation in absenteeism between participants, and the true effect of BCG vaccine.

4. Recruitment and follow-up

The RCT involves healthy, volunteer human participants able to give informed consent to participate in an interventional trial consisting in the intradermal administration of BCG vaccine standard dose or placebo (saline).

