The participants in this research are HCW. Prior to the initiation of the trial, the hospital director will inform the department heads about the trial. For recruitment we performed a rapid test (POC test) for antibodies against SARS-CoV2 using the COVID-19 IgG/IgM CTK OnSite COVID-19 IgG/IgM Rapid Test (<https://ctkbiotech.com/covid-19/>). The test is performed by collecting a drop of blood (maximum 0.4 ml of blood) from a fingerstick. The participant was informed about the POC test result and the interpretation of what it means to having or not having IgM and/or IgG antibodies. If the result is positive for IgM antibodies, we recommend that the HCP be tested for SARS-CoV2 with a swab in the throat (PCR test), according to the recommendations of local health authorities. The BCG vaccine was administered by people trained to administer vaccines by the intradermal technique. The injection site should be clean and dry. The vaccine was injected intradermally on the outer side of the upper arm, corresponding to the area of the distal insertion of the deltoid muscle (about one-third down the upper arm).

Follow-up will last for 6 months (182 days). Every second week, participants will be contacted over telephone and interviewed for symptoms and absenteeism from work. By the end of follow-up,

participants will be invited for another POC test for COVID-19 serology. The study relies on bi-weekly telephone follow-up. Participants have indicated whether they prefer to be contacted during the morning, the afternoon or at any time during the day. The responsible assistant conducts the telephone follow-up every day and introduces the data on absenteeism and causes, COVID-19 testing (if done) and their results on the WiFi-connected tablet during the interview. This data can be supplemented by daily workplace presence registry information (where present). An explicit permission for this procedure will be requested from the participant during informed consent procedures at enrolment.

5. Endpoint variables

The endpoint variables are described in Table 1

Table 1 – Definition of end-points variables

Variable	Definition	Type	Scale	Domain
Absenteeism	Refers to the total number of days absent from work due to illness	Quantitative	Numeric	In days
Absenteeism for COVID-19	Refers to the number of days absent from work due to COVID-19	Quantitative	Numeric	In days

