Primarily a descriptive analysis will be performed of all information contained in the two study groups (BCG and placebo). All variables will be analysed, one by one, to know their distribution. Background factors will be summarised by counts (percentages), means (standard deviation) or medians (interquartile range) as appropriate. Proportions will be compared using the chi-square test - χ^2 test or Fisher's Exact test (categorical variable) or Student's t-test or Mann-Whitney test (quantitative variable) according to the distribution of variables. Statistical significance was set at the 5% level (two-tailed tests) and 95% confidence intervals (95%CI) for the estimates.

The endpoints variables (table 1) will be analyzed using univariate analysis (Logrank test) and Multivariate analysis (Cox Proportional Hazard Regression, or Cox Regression), stratified by the block randomization variables gender (male/female) and occupational group (doctors/ nurses/other) in addition to site. Covariates will be tested in the model univariate, and only those that were associated with the outcome at a significance level of at least 20% will be retained in a possible multivariate model. A significance level (p-value) of less than 0.05 and its respective confidence intervals (CI) will be used.

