When you have a small sample and the numerical variable is not known to have a normal distribution (or cannot be verified satisfactorily), or when there is no homogeneity of variances, Student's t-test is not appropriate. In this situation, the nonparametric Mann-Whitney test (Wilcoxon rank-sum test, U-test) can be used. Unlike the t-test, which tests for equality of means, the Mann-Whitney test tests for equality of medians. The U values calculated by the test assess the degree of intermingling of the data of the two groups after sorting. The greater separation of the data together indicates that the samples are distinct, rejecting the hypothesis of equality of the medians. Total days of absenteeism will be analyzed using a Bayesian negative binomial regression with a fixed effect for BCG, hospital, professional category, age, enrolment week and number of average workdays per week. The excess absence of the event of interest can lead to data overdispersion (a phenomenon that occurs when the variance of the response variable is greater than the value of the mean). To check the overdispersion of the data we will use the deviance, which is also a statistic used to check the goodness of fit of the model.

The Kaplan-Meier method consists of dividing the follow-up time into intervals, whose limits correspond to the follow-up time when events occurred. The measure of association used in survival analysis to

compare groups is the Hazard Ratio (HR), with similar meaning to Relative Risk; HR is the probability that some participant who did not have the outcome event by a certain time, will have it at that time. HR therefore compares the instantaneous incidence with which events occur in the different groups (BCG and Placebo).

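### The sample size text gives a days endpoint in percent, quotes an 80% power that does not follow from its stated inputs, and gives no type-1 error or power for the Bayesian stopping rule

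*SAP*

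**What the plan says.** **Basis in days.** The protocol's Sample size section and the SAP's opening Sample size paragraph give the same inputs: 1050 randomised, 5% loss, and "a mean number of days off work due to illness in the control group of 5 days (SD=5) over a 6-month period". The protocol says this "will demonstrate a reduction among BCG vaccinated of 20% for a mean absence of 4 days (80% power and alpha 0.05"). The SD is given for the control group only.

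**Basis in percent.** SAP section 3 takes a minimum of 1000 from an outside group, without its inputs. It continues: "We decided include 350 participants per site(Cape Verde, Guinea Bissau and Mozambique) which adds 1050 participants", and calls the total "near enough to show significance for the primary outcome - expected absenteeism reduction from 5% to 4" per cent. It states no SD, alpha or power. It adds that "the final follow-up duration is subject to the percentage of absenteeism during the study period".

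**Text that conflicts with section 3.** The SAP's Trial design paragraph says Cape Verde was not authorised and that the two remaining countries went from 350 to 525 each. SAP section 4 says "Follow-up will last for 6 months (182 days"). The same section 3 page defines absenteeism in days.

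**Analysis and error control.** SAP 6.4 says "Total days of absenteeism will be analyzed using a Bayesian negative binomial regression with a fixed effect for BCG"; SAP 6.1 says "Statistical significance was set at the 5% level (two-tailed tests"). The protocol's data analysis text refers to its interim analysis section for type-1 error control and power. That section orders monthly analyses by site and combined, beginning once 200 participants are recruited. It stops the trial if, at an interim, the posterior probability that the relative risk is below 1 exceeds 0.995. It gives no number of looks, prior, final threshold, type-1 error or power.

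**The concern.** The SAP section that should settle the sample size gives the effect in a unit the endpoint does not have. A reader who took it as a share of participants would compute a very different power. The power that is stated elsewhere cannot be traced: it is paired with a conventional alpha, the inputs shown give a higher figure, and the primary analysis is a Bayesian rule with repeated looks to which that alpha is never tied.

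The false-positive rate of the rule that will decide the trial is therefore unknown to a reader. It depends on two choices that the text leaves open or ambiguous: the threshold at the final analysis, and whether a crossing in one site's data counts. Choices of this kind made after results by arm are known invite the charge that they were data-driven.

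**Working it through.** **Inputs from the documents.** 1050 randomised 1:1, 5% loss, means 5 and 4 days, control SD 5, two-sided 0.05. Analysed: 1050 × 0.95 = 997.5, or 498.75 per arm.

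**Step 1. Attempt to reproduce 80% with a fixed test.**

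- *Two means, SD 5 in both arms.* z = 1 / (5 × √(2/498.75)) = 3.158. Power = Φ(3.158 − 1.960) = 88.5%.
- *Negative binomial, same dispersion in both arms.* Variance = mean + mean²/k, so 25 = 5 + 25/k and k = 1.25. SE(log RR) = √((1/5 + 1/4 + 2/1.25)/498.75) = 0.0641. z = 0.2231/0.0641 = 3.481. Power = Φ(1.521) = 93.6%.
- *Negative binomial, SD 5 in both arms.* In the BCG arm 25 = 4 + 16/k, so k = 16/21 = 0.76. SE = √((0.2 + 0.8 + 0.25 + 1.3125)/498.75) = 0.0717. z = 3.113. Power = Φ(1.153) = 87.6%.

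Neither obvious variant recovers 80%. One-sided 0.05 gives 93.5% for two means, and ignoring loss gives 90.0%. For two means, 80% would need an SD of about 5.64. On the stated inputs 80% needs 393 per arm, so 786/0.95 ≈ 828 randomised (two means), or 324 per arm, so 648/0.95 ≈ 682 (negative binomial, k = 1.25).

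**Step 2. The percent wording.** If 5% and 4% were proportions of participants: SE = √((0.05 × 0.95 + 0.04 × 0.96)/498.75) = 0.0131; z = 0.01/0.0131 = 0.76; power = Φ(0.76 − 1.96), about 12%. If they were shares of working days, the documents give neither the number of working days nor an SD on that scale.

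**Step 3. The 0.995 rule (illustration only).** Assumptions not in the documents: a flat prior, so 0.995 corresponds to Z > 2.576; 6 to 18 equally spaced looks; 0.995 at the final look as well. Z paths were simulated with final drift 0 (error) or the z values from Step 1 (power). Sites were taken as the two countries, since the interim section speaks of two sites; the site-level column uses an equal split.

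| Looks | One-sided error, combined only | Error if either country's crossing also counts | Power, two means | Power, NB, SD 5 both arms | Power, NB, k = 1.25 |
|---|---|---|---|---|---|
| 6 | 1.8% | 4.4% | 77% | 76% | 85% |
| 10 | 2.4% | 5.6% | 78% | 77% | 86% |
| 12 | 2.6% | 6.1% | 79% | 78% | 87% |
| 18 | 3.1% | 7.3% | 80% | 79% | 87% |

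Power columns are for combined looks only. A 250/800 split gives 4.3–7.1% in the site-level column. If 0.975 applied at the last combined look, error would be 3.4–4.4% (combined only) or 5.5–8.3% (with site crossings), and negative binomial power with k = 1.25 about 94%.

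**Step 4. Site targets.** 3 × 350 = 2 × 525 = 1050, so the stale split does not change the total. Protocol Table 2 lists 100 + 150 = 250 eligible in Mozambique, against a target of 525. The table's total is 1050 + 250 = 1300.

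**The case against.** The strongest reply is that 80% at alpha 0.05 may be a fair summary of the design actually planned. In the table above, 10 to 12 combined looks give a one-sided error near 2.5% and power of 77–87%, a range that contains 80%. A single negative binomial test at 0.995 gives Φ(3.481 − 2.576) = 81.7%. The figure may also come from the outside group's calculation, whose inputs are not shown. This stands: a reader might infer from the 88–94% that 80% cannot be the power of the planned analysis, and the documents do not support that. What remains is that the text attaches 80% to a plain alpha of 0.05 and never links it to the 0.995 rule.

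Several items are also softened elsewhere. The days basis appears earlier in the SAP, the SAP explains Cape Verde's removal, and the total is unchanged. The variable follow-up sentence appeals to the adaptive design and can be read as early stopping. The protocol's risk section allows for further hospitals if recruitment falls short. These points make the section 3 faults errors of consistency, but they leave the text contradictory.

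On site-level stopping, the protocol also describes a cross-trial meta-analysis after a significant result, with a recommendation to continue if the effect is not confirmed. The error figures above do not model that step. It governs a recommendation across trials and does not amend this trial's own stopping sentence, which comes straight after the instruction to analyse each site and covers a crossing at whichever interim analysis.

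**Conclusion.** The point holds as a fault of traceability and of missing operating characteristics. Three things are established from the text: section 3 gives the wrong unit, a superseded split and a follow-up sentence at odds with 182 days; the stated 80% does not follow from the stated inputs (88–94% for a fixed test); and the cross-reference for type-1 error and power leads to a section that gives neither.

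A reader might go further in either direction. One might conclude that the trial is comfortably powered; but the 88–94% belongs to a test without interim looks, and under 0.995 throughout two of the three power calculations fall at or slightly below 80%. One might conclude from the percent wording that power is only 12%; but the endpoint and the other two sample size statements are in days. Neither reading is supported.

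The fixed-test figures rest on the documents' inputs plus an assumption about the BCG-arm variance. The stopping-rule figures (one-sided error about 2–3% for combined looks, about 4–7% if site crossings count, at 0.995 throughout) rest on assumed looks, spacing, prior and final threshold. They show the size of the ambiguity and are not estimates for this trial. The Mozambique mismatch is minor and does not show the total of 1050 to be at risk.

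**What to change.** - **SAP section 3.** Replace the percent effect with 5 to 4 days (SD 5) over 6 months. Delete the 3 × 350 sentence. Reconcile the variable follow-up sentence with the 182 days in section 4.
- **Sample size paragraphs in both documents.** Replace the bare 80% power and alpha 0.05 with power and type-1 error simulated under the planned negative binomial model, using the actual looks, prior and final threshold. State the dispersion assumed in each arm. If the fixed-test figures (about 88% for two means, about 94% for negative binomial with k = 1.25 in both arms) are also quoted, label them as a reference without interim looks and not as the power of the planned design.
- **Protocol interim analysis section.** State that the efficacy conclusion rests on the combined data only, or include site-level crossings in the simulated error. Fix the final posterior threshold before the final unblinded analysis. Inclusion began in December 2020 and absenteeism by arm goes to the DSMB monthly, so the record should also state who had seen results by arm when these choices were made.
- **Minor.** Reconcile the Mozambique target of 525 with the 250 eligible in Table 2.

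The cost is text and one simulation, with no change to the target of 1050. The quoted power may rise or fall slightly. The illustrative ranges above should not be copied into the plan.

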An insurance for the clinical trial participants will be contracted. This insurance provides cover for damage to research subjects through injury or death caused by the study. Participants will not be compensated for participating in this study. Damage to subjects through injury or death, caused by the study or negligence of local study investigators, is not accountable to the principle investigator.

Follow-up

Follow-up will take place every second week through telephone interview and by checking register of attendance at the worksite (where available). 6 months after recruitment, the participant will be invited to the study site for a new POC test for SARS-CoV2 antibodies and to answer an end-questionnaire. The participant will be informed of the result of the test. The participant will also be informed of the intervention he/she received.

The telephone contact information of the participant will be shared only with the research assistant responsible for doing the follow-up.

Protection of personal data

This research involves data collection and processing of sensitive personal data, tracking of participants and further processing of previously collected personal data (data on immunization).

Because the study comprises follow-up of participants after administration of the intervention, data cannot be anonymised. As so, data pertaining to participants will be stored in a locked room in the institution responsible for the RCT in each country (ICSM in Mozambique and Bandim Health Project in Guinea-Bissau) in one computer not connected to the internet and protected by a password. The password will be only known by the PI, Co-PI and the study supervisors.

Data analysis will be conducted by the IHMT. Personal data include: eligibility criteria, baseline characteristics, adverse events of intervention, work absenteeism and reasons, hospitalization.

Several investigators across the world have set up trials of BCG vaccination among health care workers. Until today, >20 trials are ongoing or in preparation.

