Data will be reported quantitatively. All analyses will be performed from the intention-to-treat principle. Missing data on background variables will be dealt with by multiple imputation. Final data analysis will begin when the last participant in the multicentric RCT has completed the follow-up period. The primary endpoint, work absenteeism due to illness, will be reported as the total number of sick days with standard deviation. Continuous baseline characteristics will be reported as means with the standard deviation or medians with the inter-quartile range, as appropriate. Categorical baseline characteristics will be reported as count and percentage. Statistical testing for baseline characteristics will be performed. Days of absenteeism will be analysed using a Bayesian negative binomial regression with a fixed effect for BCG, hospital, professional category, age, enrolment week and number of average workdays per week. Incidence data will be analysed in Cox proportional hazards models. Monthly, data on absenteeism by randomization group will be reported to the DSMB.

Trial registration

The trial is registered at clinicaltrials.gov. (<https://clinicaltrials.gov/ct2/show/NCT04641858>)

Funding

EDCTP is funding the run-in costs for the BCG-COVID-RCT, including trials in the respective countries and for training and management.

Study management, monitoring and quality control

The project is led by an International Steering Committee (ISC) consisting of PIs in each of the five countries involved: [name] (international coordinator), PI from Denmark; [name], PI from Guinea-Bissau; [name], PI from Portugal; [name], PI from Cape Verde; and [name], PI from Mozambique. The overall coordination is the responsibility of the Danish partner. The leader has extensive leadership experience from running a Center of Excellence in Denmark and the research group of the Bandim Health Project in Bissau for many years. The Bandim Health Project has a history of past collaboration with the Portuguese partner. The research group will hold teleconferences at least once a week with a formal pre-established agenda on training, enrollment, follow-up, losses to follow-up, staff turnover, vaccine logistics, quality control of data collection, data entry and database management, interim analysis, communication and dissemination activities, other risks. Decisions from each meeting are recorded by the coordinator.

2. Definitions

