2.2. Analyzed populations

The clinical trial participants are 1,050 HCW (definition below) recruited from hospitals in two different African countries.

The Guinea-Bissau arm of the BCG-COVID-RCT study is conducted in Bissau, the country capital, by the Bandim Health Project (BHP). The team is led by [name]. Inclusions commenced in Guinea-Bissau on December 3rd, 2020, in the Hospital Nacional Simão Mendes. After concluding inclusions at Simão Mendes, inclusions were commenced at other hospitals and health centers.

In Mozambique, this study is being conducted at Manhiça District Hospital (MDH) and Mavalane General Hospital (MGH) by the Centro de Investigação em Saúde de Manhiça (CISM) through the team led by [name]. Manhiça District Hospital is located on the main National Road One, in the capital of the Manhiça district, Maputo Province, southern Mozambique. Manhiça is a rural area located approximately 80km away from the capital, Maputo city; has a total population close to two hundred thousand people. MDH is the referral hospital with more than 100 beds and absorbs the largest proportion of HCW within the district. MGH (260 beds) is located in the district of neighborhood of Mavalane, in Maputo city (Southern Mozambique). The MGH is part of the three general hospitals of the city of Maputo. The health

area of Mavalane is the largest in the city and serves an estimated population of 609.889 inhabitants, about 50% of the health population of the capital of nation capital.

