6.1. General statistical methodology

The database system for both inclusion procedures and follow-up is REDCap (www.project-redcap.org), and the instruments have been developed by the Institute of Hygiene and Tropical Medicine at NOVA University.

Data entry for both inclusion and follow-up procedures is conducted online using the browser version, which means that no participant data is stored locally and that the study responsible(s) can monitor the data collection in real-time.

The randomization code was developed by the trial statistician, [name]. This code produces an allocation table for all the stratification layers and all the sites, with block sizes varying randomly between 4 and 6 within each individual stratum. The allocation table used for the study has not been seen and is not available to any of the researchers involved in the study and it was implemented by an independent statistician, [name], in Bissau.

From the databases of the trials in Guinea-Bissau and Mozambique, their analysis will be performed by either STATA version 17 software (Stata, College Station, TX) or SPSS version 26.

The combined data analysis will begin when the last participant in the multicentric RCT has completed the follow-up period or after the 182 day of the study and data has been cleaned.

Descriptive statistical techniques (absolute and relative frequency distribution) will be used to analyze the quality of the database through the evaluation of two aspects: completeness (field filling) and consistency (consistency between the categories marked in two related fields). The completeness indicator will be calculated as the proportion of filled fields in relation to the total of records, in percentage. Regarding completeness, the results will be categorized as the percentage of records without filling out as follows: excellent (<10% of records without filling out), regular (11 to 30%) and low (>30% of records without filling out).

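### SAP section 3 leaves follow-up length open and SAP 6.1 adds a study-day-182 analysis trigger; both conflict with the fixed 182 days per participant

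*SAP*

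**What the plan says.** **Length of follow-up.** SAP section 3 (Sample size) states: "As this is an adaptive study, the final follow-up duration is subject to the percentage of absenteeism during the study period". It then adds "variation in absenteeism between participants, and the true effect of BCG vaccine" as further determinants. The SAP synopsis (Follow-up), SAP section 4 and the Protocol's Follow-up section each give a fixed length: "Follow-up will last for 6 months (182 days". The Protocol's Ethics part (Follow-up) starts the clock at each person's entry: "6 months after recruitment, the participant will be invited to the study site". The sample-size paragraph in both documents assumes a control mean of 5 days (SD 5) over six months.

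**Start of the final analysis.** The SAP synopsis (Statistical analysis) and the Protocol (Data analysis) share one trigger: "Final data analysis will begin when the last participant in the multicentric RCT has completed the follow-up period". SAP 6.1 gives two for the combined data, namely when the last participant "has completed the follow-up period or after the 182 day of the study and data has been cleaned".

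**Adaptive rule.** The only operational one is in the Protocol (Interim analysis). Looks are monthly, and the trial stops if the posterior probability that RR < 1 exceeds 0.995. The SAP text available for review does not repeat this; its synopsis only sends monthly absenteeism data by arm to the DSMB. Neither document gives a rule for lengthening or shortening follow-up.

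**The concern.** Both sentences stand in the current SAP, and each would produce a different primary dataset if followed. Under the section 3 sentence, the outcome window is not settled in advance. Under the second trigger in SAP 6.1, anyone enrolled after the first day of the study could be analysed before reaching their own day 182.

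The primary endpoint is sensitive to this because it is a total count of sick days. The regression in SAP 6.4 has terms for BCG, hospital, professional category, age, enrolment week and average workdays per week, with no stated offset for time observed. A person seen for 90 days and a person seen for 182 days would contribute totals to the same model as if they were the same quantity. The result would also no longer correspond to the six-month mean on which the trial was sized.

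**Working it through.** **1. The plan's own figure and its time base.** Inputs from the sample-size paragraph: means 5 and 4 days, SD 5, over six months, alpha 0.05, power 80%, 5% loss, 1:1 allocation. SAP 6.1 sets two-tailed tests.

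- n per arm = 2(1.96 + 0.842)² × 5² / 1² ≈ 393, so 786 in total; 786 / 0.95 = 828.
- The plan's 1050 is not reproduced. SAP section 3 explains it as 3 × 350 set against an outside minimum of 1000. It exceeds 828, and this point does not depend on it.
- With 1050 and 5% loss, 1050 × 0.95 / 2 = 498.75 per arm. The standard error is 5√(2/498.75) = 0.317, z = 1/0.317 = 3.16, and power = Φ(3.16 − 1.96) = 88.5%. This holds for a full six-month window only.

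**2. The passages side by side.**

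| Item | Fixed statement | Conflicting statement |
|---|---|---|
| Follow-up length | 182 days (SAP synopsis, SAP 4, Protocol Follow-up), from recruitment (Protocol Ethics) | Depends on absenteeism, its variation and the BCG effect (SAP 3) |
| Final analysis | Last participant complete (SAP synopsis, Protocol Data analysis) | The same, or after study day 182 and cleaning (SAP 6.1) |

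The two triggers coincide only if everyone is enrolled on the first day.

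**3. Calendar illustration.** SAP 2.2: "Inclusions commenced in Guinea-Bissau on December 3rd, 2020". Adding 182 days gives 3 June 2021 (2 June if the first inclusion counts as day 1). The Protocol (Ethics) dates Mozambique's national approval to 11 March 2021. From then to 3 June is 20 + 30 + 31 + 3 = 84 days. A Mozambican participant enrolled after that approval would have at most 84 of 182 days (46%). The SAP synopsis plans 525 participants in that country.

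**4. Share of planned person-time seen at study day 182.** The documents do not give the accrual period A, so uniform accrual is assumed and a range shown. For A ≤ 182 the share is (182 − A/2)/182; for longer A it is (182/A) × 91/182.

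| A (days) | Share observed | Last participant finishes, study day |
|---|---|---|
| 30 | 92% | 212 |
| 91 | 75% | 273 |
| 182 | 50% | 364 |
| 365 | 25% | 547 |

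**5. Power if the window were shortened for everyone.** Let f = d/182, keep the 20% relative effect and 498.75 per arm, so the difference in means is f. The documents give an SD only for six months, so two assumptions are shown: (a) SD = 5√f; (b) constant negative binomial dispersion (25 − 5)/25 = 0.8, so SD = √(m + 0.8m²) with m = 5f.

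| Window (days) | Power (a) | Power (b) |
|---|---|---|
| 182 | 88.5% | 88.5% |
| 121 | 73% | 85% |
| 91 | 61% | 82% |
| 61 | 45% | 76% |

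These rows apply to one common shorter window, not to the mixture of windows in step 4.

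**The case against.** The strongest reply is that both sentences are loose wording and not rules. Nobody can choose a window by a true effect, which is unobservable. The quantities listed in section 3 do govern when a sequential trial crosses its boundary, so the sentence may be a clumsy reference to the Protocol's early-stopping rule. That reading is possible. However, the sentence names follow-up duration, and the SAP text available contains no stopping threshold for it to refer to.

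Likewise, day 182 in SAP 6.1 may have been meant as each participant's day 182. The alternative introduced by the 'or' is then redundant, and the text still says day 182 of the study. It needs correcting on either reading.

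The 3 June 2021 scenario is illustrative. The Protocol is dated 20 January 2022, after that date, and SAP 2.2 describes the Mozambican work as under way. The clause also requires cleaned data, so an analysis would not begin on day 182 itself.

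It is fair to add that the enrolment-week term could absorb part of the difference in observed time under a common calendar cut-off, depending on how it is coded, which is not stated. It would not turn truncated counts into six-month totals.

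A reader might infer optional stopping and an inflated type I error. The documents do not support that. Neither provides for looking, extending follow-up and re-testing at an unadjusted 5%; the only adaptation is early stopping at 0.995. A calendar trigger does not depend on the data, and SAP 2.1 says the analysts are blinded.

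**Conclusion.** The contradictions are real and should be corrected. One SAP sentence makes the outcome window variable against three statements of 182 days, and one SAP clause adds an analysis trigger that the SAP synopsis and the Protocol do not have.

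The size depends on accrual, which the documents do not give. Under uniform accrual, the literal second trigger would capture between 92% (30-day accrual) and 25% (365-day accrual) of planned person-time. From the stated dates, Mozambican follow-up would be at most 84 of 182 days, assuming no enrolment there before national approval. The consequence is truncated totals in a model without a stated offset, and a departure from the six-month basis of the sample size. No error-rate figure is warranted.

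Nothing in the documents shows that either clause was acted on, so it would be wrong to infer that the Mozambican data were in fact cut short.

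**What to change.** - **SAP section 3:** delete the adaptive-duration sentence, or replace it with a cross-reference to the Protocol's interim stopping rule (posterior probability above 0.995). State that follow-up is 182 days per participant from recruitment.
- **SAP 6.1:** delete the alternative trigger based on study day 182. The final analysis then starts when the last participant completes 182 days, or when the trial stops under the interim rule.
- **SAP 6.4:** state that, if the trial stops early, log observed person-time enters the negative binomial model as an offset, since some participants will then have fewer than 182 days.

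The cost is two sentence edits and one added sentence. No new data and no design change are needed. The edits should be made before any unblinded analysis.
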